PregSourceSM: Crowdsourcing to Understand Pregnancy Observations of Daily Living from Pregnant Women

Protocol Number: T-CH-0901: PregSourceSM

ClinicalTrials.gov number: NCT02577536

Lead Study Investigator: [name], MPH
Deputy Director, Division of Extramural Research, NICHD
[name]
[name]
[contact]
[contact]

Associate Investigator(s): [name], NICHD
[name], MA, NICHD
[name], NICHD
[name], JD, NICHD
[name] PhD, NICHD

Research Coordinator(s): [name], MS CGC MBA, PatientCrossroads, Inc.
[name], MS, PatientCrossroads, Inc.

Version Date: 2015 December 8

Protocol Details

Total requested accrual	100,000 Subjects (estimated)
Project Uses Ionizing Radiation:	No
IND/IDE required:	No
Durable Power of Attorney	No
Multi-institutional Project	No
Data and Safety Monitoring Board:	No
Technology Transfer Agreement:	No
Samples are being stored:	No
Flesch-Kincaid reading level of consent form:	8.0

Contents

Abstract	6
Section 1. Statement of Problem	7
Section 2. Study Objectives and Outcome Measures	11
2.1. Primary Objective	11
2.2. Secondary Objectives	11
2.3. Outcome Measures	12
2.3.1. Primary Outcome Measures	12
2.3.2. Secondary Outcome Measures.....	13
Section 3. Study Population.....	14
3.1. Inclusion Criteria.....	14
3.2. Exclusion Criteria	14
Section 4. Study Design and Methods.....	15
4.1. Study Overview	15
4.2. Recruitment	15
4.2.1. Recruitment Strategy	15
4.2.2. Recruiting Non-English Speakers	16
4.2.3. Recruitment Advertising.....	17
4.2.4. Anticipated Accrual Rate.....	18
4.2.5. Recruitment Replacement Strategy.....	18
4.3. Screening	18
4.4. Study Procedures.....	19
4.4.1. Consent Documents and Process	19
4.4.2. Account Profile Set up and Health History Questionnaire	19
4.4.2.1. Trackers	20
4.4.2.2. Gestational Age Questionnaires.....	22
4.4.2.3. Sub-group Questionnaires	22
4.4.2.4. Future Modules.....	23
4.4.3. End of Participation	23
4.4.4. Follow-up	23
4.4.5. Other Clinical Trials and Studies	23
4.4.6. Beta Testing.....	24
Section 5. Storage of Data And Samples	25
5.1. Study Data Storage	25
5.2. Data Sharing.....	25
5.3. Data Disposition.....	25
5.4. Study Samples Storage and Disposition	26

5.5.	Additional Considerations	26
5.5.1.	Research with Investigational Drugs or Devices.....	26
5.5.2.	Gene Therapy.....	26
Section 6.	Potential Risks and Benefits	27
6.1.	Known And Anticipated Risks and Discomforts.....	27
6.2.	Steps Taken to Minimize Risk	27
6.2.1.	Data Security.....	27
6.2.2.	Contacting Subjects about Other Clinical Studies	27
6.2.3.	Sharing De-identified Data with Other Researchers and/or Data Repositories.....	28
6.3.	Classification of Risk.....	28
6.4.	Anticipated Benefits	28
6.4.1.	Direct Benefits.....	28
6.4.2.	Indirect Benefits.....	28
Section 7.	Subject Safety Monitoring	30
7.1.	Study Monitoring Plan	30
7.1.1.	Data and Safety Monitoring Plan and Stopping Rules.....	30
7.1.2.	Procedures for Suspending or Stopping Enrollment	30
7.2.	Quality Assurance	31
7.2.1.	Monitoring Participant Burden..... Error! Bookmark not defined.	
7.2.2.	Monitoring the Participant Registration Process	31
7.2.3.	Monitoring Participant Burden.....	31
7.2.4.	Monitoring Recruitment and Demographic Distribution	32
7.2.6.	Lost to Follow-up	32
7.3.	Reporting of Unanticipated Problems, Adverse Events and Protocol Deviations	33
7.4.	Criteria for Individual Subject Withdrawal from the Study.....	33
Section 8.	Statistical Analysis Plan.....	34
8.1.	Analysis of Data/Study Outcomes	34
8.2.	Sample Size, Power Analysis, and Available Population	34
8.3.	Projected Recruitment Time.....	34
Section 9.	Human Subjects Protection	35
9.1.	Subject selection.....	35
9.1.1.	Statement of Equitability	35
9.2.	Justification for Inclusion of Vulnerable Subjects.....	35
9.3.	Safeguards for Vulnerable Populations	35
9.4.	Qualifications of Investigators	35
9.4.1.	Lead Study Investigator	35
9.4.2.	Associate Investigators	35
9.4.3.	Coordinators	36

9.5.4.	Required Human Subjects Training	36
9.5.	Consultant Experts	36
9.6.	Alternatives to Participation.....	37
9.7.	Confidentiality.....	37
9.7.1.	Confidentiality of Research Data	37
9.7.2.	Certificate of Confidentiality.....	38
9.7.3.	Privacy Policy and Terms and Conditions of Use	38
9.8.	Conflict of Interest	38
9.9.	Research and Travel Compensation	38
Section 10.	References	39

ABSTRACT

Objective

To better understand the range of physical and emotional experiences and alterations in behavior that women have during pregnancy and after giving birth, the impact of these experiences on women's lives, and the perinatal challenges encountered by special sub-populations of women.

Study Population/Eligibility Criteria

Pregnant women age 18 to 70, all races and ethnicities.

Design Type

PregSourceSM: Crowdsourcing to Understand Pregnancy (PregSourceSM) will use a longitudinal, crowd-sourcing, citizen science approach, asking pregnant women regularly and directly about their pregnancies. Participants will enter information throughout gestation and the early infancy of their babies into online surveys and trackers via a website and/or mobile applications ("apps"). In exchange, participants will be able to track their pregnancy data over time, print out reports to share with their healthcare team, and view summaries of de-identified data to see how they compare to other women. In addition, PregSourceSM will provide participants with links to trusted, evidence-based information from partner organizations about pregnancy management, issues, and complications.

Participants may also be a potential pool of recruits for clinical studies. Based on information they enter, eligible women who are interested in participating in clinical studies may be sent contact information about observational or interventional studies. Their contact information will not be shared directly with researchers.

After a critical mass of data is collected, de-identified data will be available to approved researchers for analysis.

Outcome Measures

PregSourceSM is an online research registry for collecting information about the natural history and range of normative experiences of pregnancy from the primary source: pregnant women. It, therefore, does not have specific outcome measures beyond descriptive data on women's experiences and pregnancy outcomes.

SECTION 1. STATEMENT OF PROBLEM

In 2009, the U.S. Centers for Disease Control and Prevention (CDC) reported an estimated 6,369,000 pregnancies – 102 pregnancies per 1,000 women – resulting in 4,131,000 live births and 1,087,000 fetal losses (Curtin SC, et al 2013). While many of these women are seen by physicians, and hundreds of research studies are conducted, we know more about pregnancy complications, than about the natural history of human pregnancy. There is limited to no information on normal pregnancy despite its prevalence as the majority of studies are performed on specific conditions. Furthermore, even those tend to be case series and not representative of the population. In a review of clinicaltrials.gov there are no ongoing studies characterizing normal pregnancy. Information collected in any systematic way from the patient's point of view about how pregnancy affects the lives of women in our modern world is also missing, such as:

- How many women get morning sickness? How long does it generally last? At what gestational ages does it tend to occur? Does it have any impact on maternal weight?
- How does being pregnant affect women's sleep, energy levels, and mood? How do these change over the course of the pregnancy?
- What is the impact of pregnancy and pregnancy symptoms on women's lives? How easy is it to stick to your doctor's orders for diet, exercise, and special treatments?
- How is being pregnant more challenging for certain women (e.g., women with physical and intellectual disabilities)?

We believe that PregSourceSM: Crowdsourcing to Understand Pregnancy (PregSourceSM) will help us gather information directly from pregnant women as they experience it, so that we can help answer some of these questions. According to Project HealthDesign, "Lay people engage in health practices and health behaviors every day, not just during visits to clinicians. They revealed that they attend not only to signs and symptoms of illness as directed by clinicians, but also to the idiosyncratic, highly personal thoughts, behaviors, attitudes, sensations, and environmental conditions that inform them about their health state and alert them to take action related to health. These observations of daily living (ODLs) complement traditional signs and symptoms of disease (e.g., blood pressure, shortness of breath) and highlight the personal experience of health and disease (Brennan 2010)."

PregSourceSM is an initiative run by the *Eunice Kennedy Shriver* National Institute of Child Health and Human Development, to learn about women's experiences with pregnancy, to collect observations of daily living and healthcare information about their pregnancies. It is an online research registry for collecting information about the natural history and range of normative experiences of pregnancy from the primary source: pregnant women. Its goal is to collect data that will help inform future studies on pregnancy and other health areas, which we discuss below in more detail. It is neither designed nor intended to determine clinical effectiveness or cost-effectiveness of health care products and services, measure or monitor safety and harm,

measure quality of care, or diagnose or treat any disease or condition. The purpose of PregSourceSM is to inform future research – not necessarily to perform empirical research – by learning about:

- Women's physical and emotional experiences during pregnancy and after giving birth;
- How pregnancy affects their lives; and
- Special challenges of some women, such as women with disabilities or chronic health conditions.

PregSourceSM can give us an overall picture of what women experience during pregnancy based on information from the women themselves.

Crowdsourcing Methodology

To do this, PregSourceSM will harness the innovative power of crowdsourcing and citizen science (Swan M 2012) by asking pregnant women to contribute their personal observations of daily living to our database. Promoted recently by the White House Office of Science and Technology Policy (OSTP), “Crowdsourcing is a process in which individuals or organizations request voluntary contributions from a large group of unknown individuals (“the crowd”)(The White House, Web log post, December 2, 2014).” OSTP includes initiatives that incorporate and improve upon crowdsourcing as part of the Second Open Government Federal Action Plan. The Office also notes that “Citizen science and crowdsourcing are powerful tools that can help Federal agencies: advance and accelerate scientific research through group discovery and co-creation of knowledge; increase science literacy and provide students with skills needed to excel in science, technology, engineering, and math; improve delivery of government services with significantly lower resource investments; and connect citizens to the missions of federal agencies by promoting a spirit of open government and volunteerism.” PregSourceSM is designed to do all of these.

PregSourceSM will use a longitudinal, crowd-sourcing, citizen science approach, asking pregnant women directly about their pregnancies. Participants will enter information throughout gestation and the early infancy of their babies into online surveys and trackers via a website and/or mobile applications (“apps”). This research registry will enable us to collect data and experiential trends on issues and topics for which no baseline data currently exist, and that can inform current and future research projects among pregnant women (Wang et al 2015). Because of the Internet-based design of the study, it may not enroll a nationally representative sample. But by surveying a broad cross-section of women about their experiences in near real-time, data from PregSourceSM might confirm (or contradict) some of the information that currently exists about pregnancy topics such as nausea, weight gain, and sleep quality and duration. For instance, one of the key findings from the 2009 IOM pregnancy weight gain guidelines were that “Currently available data sources are inadequate for studying national trends in GWG [gestational weight gain], or postpartum weight, or their determinants (IOM 2009).” PregSourceSM can provide data on GWG trends and other baseline data that investigators can use to inform their observational studies and interventional trials on such topics and can potentially aid in recruitment.

By collecting information directly from the primary source (pregnant women), PregSourceSM requires minimal infrastructure cost, while simultaneously maximizing delivery of evidence-based pregnancy information from experts.

Participants answer questionnaires about their experiences over the course of their pregnancy, recovery, and their baby's development – observations of daily living that are usually available only from periodic, time-constrained clinical visits. Women with certain pre-pregnancy conditions (e.g., physical disabilities) and those who develop pregnancy complications (e.g., gestational diabetes) will be asked additional questions about their pregnancy experiences, outcomes, and recovery. The anytime/anyplace access to participants improves data collection by recording events as they occur throughout pregnancy. This type of access to participants in research is unprecedented and not feasible in other types of research designs.

In addition to utilizing the power of the crowd, PregSourceSM aims to capitalize on the new trend of the “quantified self,” people aiming to improve their personal health by using technology to record their daily activities and biometrics. Many women now are currently tracking their menses, fertility, and other health data using apps, wearable devices such as FitBit and Apple Watch, and other websites (Swan M 2009, Wolf G 2009, Appelboom G et al 2014). Given the 300+ pregnancy-related apps currently available, we believe that pregnant women are particularly interested in tracking their data. We also believe that they will be willing to donate their data for scientific research, if we: provide them with easy-to-use trackers and questionnaires, and incentivize them to keep using them over the course of their pregnancy with educational materials, comparison summary data, and tools that capture what they are interested in tracking, in addition to data that are of empirical research value. Finding out how many women are willing to do so, and best practices and lessons learned along the way, in and of itself, will provide meaningful information for future crowdsourcing research efforts in pregnancy and other health areas.

In exchange, participants will be able to track their pregnancy data over time, and print out reports to share with their healthcare team. They will also be able to view summaries of PregSourceSM data to see how they compare to other women – “Am I the only one that still has morning sickness at 6 months of pregnancy?” In addition, PregSourceSM participants will receive relevant information about evidence-based medical guidelines and practices that are already published by government and non-government health care societies and organizations. Participants will be clearly told that if they have any concerns about their pregnancy or about what they learn in PregSourceSM, they should discuss their concerns with their health care provider.

Participants may also be a potential pool of recruits for clinical studies. Based on information they enter, eligible women interested in participating in clinical studies, would be sent contact information about observational or interventional studies. Their contact information will not be shared directly with researchers.

After a critical mass of data has been collected, de-identified data from PregSourceSM will be made available to approved researchers for analysis. De-identified data will be housed in the Research Data Patient Repository (RDPR).

By gathering information directly from pregnant women, researchers will have access to a large dataset to better understand pregnancy from the participant's point of view and potentially find ways to improve healthcare and wellness for all pregnant women.

SECTION 2. STUDY OBJECTIVES AND OUTCOME MEASURES

2.1. PRIMARY OBJECTIVE

To better understand the range of physical and emotional experiences and alterations in behavior that women have during pregnancy and after giving birth, the impact of these experiences on women's lives, and the perinatal challenges encountered by special sub-populations of women. The protocol will be positioned to address numerous questions. Initially, it will focus on eight areas with the ability to expand to many other areas once the foundation is developed.

2.2. SECONDARY OBJECTIVES

To measure the impact that pregnancy symptoms and treatments have on women's lives.

Examples of the overarching questions and measures include:

- Nausea and vomiting during pregnancy – to identify how often this affects pregnancy, its timing, treatments, and impact on weight
 - How often and at what gestational age do nausea and vomiting begin/improve?
 - Impact on weight
 - Treatments
- Physical disabilities and pregnancy – to identify how many pregnancies may be affected by physical disabilities
 - What disability?
 - Impact on pregnancy
 - Impact of pregnancy on the condition
- Weight gain in pregnancy – to identify weight gain patterns in pregnancy and compare to Institute of Medicine guidelines
 - Pre-pregnancy weight and height
 - Weight weekly or monthly
 - Plot weight gain on the appropriate IOM guideline chart
- Activity/Exercise in pregnancy – to identify exercise patterns in pregnancy including type and amount of exercise, impact on pregnancy
 - Evaluation of moderate and high impact activities across pregnancy
- Sleep in pregnancy – to identify sleep patterns in pregnancy including number of hours, sleep quality, and sleep position
 - Sleep pattern prior to pregnancy
 - Number of hours (on average) sleep per night
 - Quality of sleep
 - Prevalence of sleep apnea
 - Sleep position
- Mood in Pregnancy – to identify general mood in pregnant women throughout gestation. This will be done via a Mood Tracker and mood may be entered as often as necessary. We will use the validated Positive and Negative Affect Schedule (PANAS)

(Watson D and Clark LA 1994; Thompson ER 2007). This measure has also been used to access psychological stress among women with and without reproductive failure (Coughlan C et al 2014). It may collect mood descriptions such as excited, irritable, angry, jittery, etc.

- Medications in pregnancy – to identify how many medications women are taking, reasons for their use, and how many are taken without clinician recommendation
 - Any medications used (weekly query) with triggers of those input in prior week to allow a continuation or stopping of that medication
 - Reason for the medication being used
 - Did a medical provider recommend the medication or is it being used over the counter?
- Alternative “medications”/herbal supplement use in pregnancy – to identify how many and what alternative medications/herbal supplements women are taking, reasons for their use, and how many are taken without clinician recommendation
 - Any herbal supplements or alternative medications used?
 - If yes, at what gestational age and for how long?
 - Reason for use
- Number of ultrasounds in pregnancy – to identify how many ultrasounds are being performed in pregnancy, the reasons, and how many are performed without clinician recommendation
 - Any ultrasounds during pregnancy?
 - Reason for the ultrasound

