2.3.2. Secondary Outcome Measures

- Proportion of pregnant women who experience nausea and vomiting in pregnancy across gestation
- Proportion of pregnancies that are impacted by physical disabilities
- Weight gain patterns in pregnancy with a comparison to IOM guidelines
- Exercise patterns in pregnancy including type and amount of exercise, impact on pregnancy
- Sleep patterns in pregnancy including number of hours, sleep quality, and sleep position
- How many medications women are taking, reasons for their use, and how many are taken without clinician recommendation
- How many alternative medications /herbal supplements pregnant women are taking, reasons for their use, and how many are taken without clinician recommendation
- Number of ultrasounds in pregnancy

In the future, additional measures may be added, such as assessments of maternal mental health, stress, chronic conditions such as hypertension and diabetes, and assessment of maternal diet and other environmental factors.

SECTION 3. STUDY POPULATION

This will be a prospective cohort study, collecting information from women of child-bearing age who are pregnant. The study will include healthy volunteers, as well as those with pre-conception medical conditions and/or pregnancy complications. Because it will be online, there is no limit to the number of participants who can join. It will be focused on women in the United States, but because it will be online, women in other countries may also participate.

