4.4.2.1. Trackers

Each participant can enter data in a set of health “trackers” – online or in-app software diaries that capture daily or weekly information over the course of pregnancy about her weight, nausea symptoms, mood, and sleep. Additional trackers may be added at a later date for tracking nutrition, exercise, and pain. She can enter data in the trackers as often as she chooses. We anticipate that for trackers such as nausea, sleep, and mood, a participant might enter data on a daily basis; while weight data might be entered only once a week or even once a month. Most trackers will collect data on timing, duration, severity/intensity, and related issues. A 2013 report by Citrix⁴, a software company that tracks app usage, shows pregnancy related apps to have wider usage. Many of the available trackers have been used and/or validated in the pregnant population⁵. Recent research articles⁶ have demonstrated the use of web-based methods to collect relevant health related information from pregnant women.

Unless otherwise indicated in her Account Profile, a participant will be reminded on a weekly basis to update her information, if she has not entered new data within the past two weeks.

³ Participants will not be required to use the apps. The apps will be available as a potentially more readily available means of accessing the questionnaires and trackers.

⁴ Nick Bilton, New York Times, August 26, 2015

⁵ Hämeen-Anttila K, Nordeng H, Kokki E, Jyrkkä J, Lupattelli A, Vainio K, Enlund H. Multiple information sources and consequences of conflicting information about medicine use during pregnancy: a multinational Internet-based survey. *J Med Internet Res.* 2014 Feb 20;16(2).

⁶ Wise LA, Mikkelsen EM, Rothman KJ, Riis AH, Sørensen HT, Huybrechts KF, Hatch EE. A prospective cohort study of menstrual characteristics and time to pregnancy. *Am J Epidemiol.* 2011 Sep 15;174(6):701-9

We anticipate including the following trackers:

Weight tracker. Weight would likely be entered weekly/monthly. Data collected includes:

- Weight (in pounds or kilograms)⁷

Nausea tracker. The Nausea Tracker could be entered as often as necessary, collecting data on:

- Date
- Timing (morning, afternoon, all day)
- Duration
- Severity (just nauseous, vomited)

Sleep tracker. In addition to asking about a participant's sleep patterns and apnea diagnosis prior to pregnancy in the initial health questionnaire, the Sleep Tracker may collect data on:

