- Number of hours of sleep each night
- Quality of sleep (slept soundly, tossed and turned, etc.)
- Sleep position (back, stomach, right side, left side)

Activity tracker. Activity could be entered as often as necessary. It may collect data on:

- Intensity of physical activity
- Duration of physical activity

Mood tracker. The Mood Tracker could be entered as often as necessary. We will use the validated Positive and Negative Affect Schedule (PANAS) (Watson D and Clark LA 1994; Thompson ER 2007). This measure has also been used to access psychological stress among women with and without reproductive failure (Coughlan C et al 2014). It may collect:

- Mood description

As per Section 7.1.1.1 Safety: "If a participant enters data indicating a health or safety concern, the database will send an automated notice to her that she may want to contact her doctor for advice. The database may also refer her to related factsheets and websites with further information." In PregSourceSM, after a participant enters data for the PANAS, the platform will calculate raw scores for both positive affect (PA) and negative affect (NA). Crawford (2010) reported norms for the PA and NA scores on the PANAS instrument. Because the data were not normally distributed, they converted the data into percentiles. The Crawford nomogram will be used to convert raw scores into percentiles. Participants who score >95th percentile for NA and/or <5th percentile for PA will be considered to have affect that deserves further attention by a clinician. Participants with scores in these ranges will receive a notification stating that their mood may indicate a problem that they may want to discuss with their care provider. Participants will also receive a follow-up message 2 weeks after the initial notification

⁷ Height data would be collected in the Initial Health Questionnaire, so that BMI can be calculated. We would ask in the Gestational Age monthly questionnaires if there was any change in height (not likely for adults, but may change for teenagers).

reminding them that their mood tracker indicated a concern that may warrant discussion with their health care provider.

Medications in pregnancy tracker. The Medications Tracker may ask if the women have:

- Taken any medications for specific conditions
- When they stopped taking the medication
- Reason for the medication being used

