4.4.2.2. Gestational Age Questionnaires

Once a month, PregSourceSM will send each participant an email, text, or app push notification, with a link to a new questionnaire relevant to her current week of gestation. For example, at 25 weeks of gestation, we may ask whether she has felt her baby move yet. At the end of each questionnaire, if the participant has not entered data into the health trackers in the past month, she will be taken to the appropriate trackers to enter information. This process will allow PregSourceSM to reduce duplication of questions, and capture changes over time in a consistent manner (e.g., all weight data will be entered into the Weight tracker).

If a participant does not complete her monthly questionnaire, she will receive a reminder once a week to do so via email or text to review the information she has entered into the database and provide any appropriate updates to her information.

Gestational-age questionnaires will continue monthly through pregnancy and then quarterly up to 36-months post-partum to capture information on maternal recovery and neonatal and infant outcomes and development.

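### The medication query carries forward only drugs entered in the prior week, so a woman returning after the gaps the protocol allows would, read literally, be shown nothing to confirm or stop

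*Protocol*

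**What the plan says.** Section 2.2 gives, as one of its example measures for medications, "Any medications used (weekly query) with triggers of those input in prior week to allow a continuation or stopping of that medication". The purpose is clear: a drug reported earlier is put back in front of the woman so that she can say whether it continues.

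Three other rules govern when she enters data:

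- Section 4.4.2.1 sets no interval for the trackers: "She can enter data in the trackers as often as she chooses".
- The same section says that, unless her profile indicates otherwise, she is "reminded on a weekly basis to update her information, if she has not entered new data within the past two weeks".
- Section 4.4.2.2 adds a check at the end of each monthly questionnaire: "if the participant has not entered data into the health trackers in the past month, she will be taken to the appropriate trackers". If she leaves that questionnaire incomplete, "she will receive a reminder once a week to do so via email or text to review the information she has entered".

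The description of the Medications Tracker in Section 4.4.2.1 says that it may ask, among other things, "When they stopped taking the medication". It mentions neither the weekly query nor the carry-forward. The related secondary outcome in Section 2.3.2 is "How many medications women are taking, reasons for their use, and how many are taken without clinician recommendation".

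**The concern.** The carry-forward looks back one week, whereas the prompts that bring a lapsed participant back work on two weeks and one month. A woman who responds to either prompt has, by the terms of the prompt, entered no medication in the prior week. If the look-back is programmed as written, she sees no earlier drug and is asked nothing about it.

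The measure at stake is the number of medications women are taking. When an earlier drug is not shown and not mentioned, the data cannot separate three states: still taken but not re-reported, stopped, and unknown. The protocol does not say which applies to a drug with no stop report. The problem falls on irregular reporters, so the quality of the medication record would vary with engagement. Section 8.2 itself says that it is hard to estimate how many women will enter data consistently, and Section 7.2.3 plans to count how many complete the weekly trackers at least once per week. Gaps are therefore expected.

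**Working it through.** No sample size, power or error rate bears on this point, and the plan gives no figure to reproduce. The check is a calendar comparison.

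Inputs:

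- Look-back of the medication query: the prior week, taken literally as 7 days (Section 2.2).
- Inactivity reminder: from 14 days without new data, then weekly, as the default (Section 4.4.2.1).
- Routing from the monthly questionnaire: one month without tracker data, taken here as 28 to 31 days (Section 4.4.2.2).
- Entry interval: the participant's choice (Section 4.4.2.1).

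Let a drug be entered on day 0 and not mentioned again. The distance by which it falls outside the window is its age at the next entry minus the look-back.

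| Next entry occurs | Age of the drug entry | Outside a 7-day window by | Shown for continue or stop? |
|---|---|---|---|
| Day 7, weekly query answered | 7 days | 7 − 7 = 0 days | Yes, if day 7 counts as within the week |
| Day 14, one weekly query missed | 14 days | 14 − 7 = 7 days | No |
| Day 14 or later, on the two-week reminder | at least 14 days | at least 7 days | No |
| After a month, on the monthly routing | at least 28 to 31 days | at least 21 to 24 days | No |

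On the literal reading, the list is filled only for women who keep up the weekly rhythm. It is empty for everyone who returns on the two-week reminder or the one-month routing, and also after a single missed weekly query.

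Two further points come from setting the sections side by side. First, the two-week reminder depends on new data in general, not on medication data. On that wording, a woman who logs mood or sleep regularly may never be reminded while her medication record lapses. Second, Section 4.4.2.1 describes the Medications Tracker without saying that earlier drugs are displayed, so nothing there supplies the list that Section 2.2 leaves out after a gap.

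**The case against.** Several things can fairly be said in the plan's defence.

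- *The wording may not be a specification.* Section 2.2 introduces its items as examples, and prior week could mean the last weekly entry, not the last seven calendar days. On that reading the list would not be empty. This stands as a genuine ambiguity, but it has to be settled before programming, and the proposed wording settles it.
- *There is a separate stop item.* A woman returning after a gap could report when she stopped a drug, whatever the look-back. This also stands in part. The item is only something the tracker may ask, no start date is listed, and nothing says that the earlier drug is displayed. Closing it then depends on her raising it unprompted.
- *There are other prompts.* The weekly reminder for an incomplete monthly questionnaire asks her to review and update what she has entered, and Section 7.2.1 has coordinators follow up inconsistent responses. The reminder runs only while the questionnaire is incomplete and is not specific to medications. A drug that is simply no longer mentioned need not look inconsistent.

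A reader might infer more than the documents support. One might conclude that duration of use is lost. It is not: earlier entries remain in the database and a stop date may be collected. Nor is duration a listed outcome for conventional medications, since Sections 2.2 and 2.3.2 name number, reasons and use without clinician recommendation. One might also expect a re-entered drug to be counted twice. No counting rule is fixed, because Section 8.1 states that there is no pre-planned analysis, and counting distinct drugs would avoid the problem. Finally, one might take the 67% in Section 7.1.1.2 as a weekly response rate and compute how often the chain of entries breaks. That figure is a threshold for reviewing a question or questionnaire, not a rate of weekly response, so it cannot be used in this way.

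**Conclusion.** The point holds as a mismatch between a one-week look-back and re-contact rules of two weeks and one month. Read literally, the continue-or-stop check is empty for every woman who returns on either rule, by a margin of at least 7 days. Current medication status and stop timing are then not reliably captured for irregular reporters, and the stop item and the review reminder only partly make up for this.

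The conclusion rests on reading prior week as seven calendar days and on the default reminder setting. The share of women affected cannot be estimated, because the protocol gives no response rate for the weekly query. The listed measure exposed is the number of medications women are taking. This is a modest design weakness that should be corrected before launch, because what is missed could later be recovered only by recall. It does not show that medication data in general will be unusable.

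**What to change.** In Section 2.2, remove the restriction to the prior week. State instead that every medication from any earlier entry not yet marked stopped is shown at the participant's next entry, however long the gap, and that for each one she is asked whether she still takes it or when she stopped. Put the same rule in the description of the Medications Tracker in Section 4.4.2.1, so that the two sections agree.

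The cost is one wording change in two places and a change to the query logic before launch. The downside is a longer list for women with many open medications.

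Using the same rule in the Alternative Therapies Tracker is optional. Section 2.2 asks how long such products are used and the tracker description lists no item for it, but no prior-week trigger is stated there, so the defect described here does not arise in that tracker.
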